- Patient continues ill and identifies his/her major problem as being one with fatigue, brain fog or widespread pain. To be included in the study, the patient must have at least one of the following: fatigue sufficient to produce a substantial decrease in activity at work, home, social or school life over the past month where substantial is 3 or higher on a 0 to 5 scale [0, none; 1, mild; 2, moderate; 3, substantial; 4, severe; 5, very severe]; brain fog producing at least a substantial burden over the past month; four quadrant pain producing at least a substantial burden over the past month.
- Sexually active women will be asked to take at home pregnancy tests if willing to participate in this trial. Pregnancy tests will be reimbursed and patients will communicate with the coordinator the results as well as show proof. We will not be testing menopausal woman or women without a sexual partner.
- Patient is 18 to 72 [upper age limit to exclude older patients who may have cover disease producing their symptoms].

Patients will sign informed consent remotely via RedCap. Patients will already have been seen by a physician who will have ruled out any medical cause for the patient's current symptoms. Patients will complete the Chalder Fatigue Scale [11 questions with four possible answers each]; Short Profile of Mood States [37 words concerning which patients provide input on a 5 point scale ranging from not at all to extremely] and the SF-36, a 36 question vehicle to determine the patient's health related quality of life.

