They will then be mailed a Parasym device and have a zoom session with research personnel to assure appropriate use. Subjects will be instructed to use the device as instructed [i.e., attached to the left tragus] for 35 min each day using a current which is not uncomfortable to use. That is, subjects can adjust the current and will asked to increase it to an intensity that is tolerable to use for the 35 min stimulation period. Patient will be able to control the duration of the stimulus. We will advise the subject to give him/herself at least 35 min of stimulation but that they can increase that duration up to an hour pending how they feel [the study on Long COVID used 35 min but in their other trials, they use 60 min].

Patients will be provided the cell number of a member of the research team and will be told to call if they have any problems or questions about the treatment or the study itself.

Patients will be called at 4 and 6 weeks after starting treatment and will again be asked to provide data on the visual analog scales concerning [1] fatigue; [2] brain fog; [3] widespread pain. They will also be asked to complete the Chalder, POMS, the SF-36 and a 7 point question on self rated current state of health [+3 very much better; 0 no change; -3 very much worse] -- Patient Global Impression of Change (PGIC).

Criteria for primary outcome: Improvement on two of the following with improvement defined as: a 0.6 SD reduction in impaired physical function on the SF-36; reduction in severity of the most troubling symptom endorsed by the patient to 0-2 on the visual analog scale [none, mild or moderate]; no longer a "case" on the Chalder; much improved or very much improved on the PGIC.

Criterion for secondary outcome: Improvement by at least 10 points on the short version of the POMS.

Criteria for successful outcome: At least a third of patients fulfill criteria for primary outcome.

At the conclusion of the study, patients will be able to keep their Parasym VNS device.

Effective Date: 3/8/2022 End Date:3/7/2023

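### The symptom component of the primary outcome needs a starting value, but the listed pre-treatment assessments omit the three symptom ratings, so the eligibility rating may serve as baseline and let some regression to the mean count as improvement

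*Protocol*

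**What the plan says.** All references are to the Protocol.

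- **Entry (Inclusion Criteria).** The patient "identifies his/her major problem as being one with fatigue, brain fog or widespread pain". At least one of fatigue, brain fog or four-quadrant pain must be substantial over the past month, "where substantial is 3 or higher on a 0 to 5 scale". The numeric scale is written out for fatigue. For the other two it is implied by the word substantial.
- **Before treatment (paragraph after Inclusion Criteria).** "Patients will complete the Chalder Fatigue Scale [11 questions with four possible answers each", followed by the short POMS and the SF-36. The list has no rating of the three symptoms on the scale used for the outcome. The Chalder measures fatigue, but it is a different instrument and feeds a different component.
- **Before first use.** Patients "have a zoom session with research personnel to assure appropriate use".
- **Follow-up calls at 4 and 6 weeks.** Patients "will again be asked to provide data on the visual analog scales" for fatigue, brain fog and widespread pain.
- **Criteria for primary outcome.** "Improvement on two of the following with improvement defined as" any of four components, one of which is "reduction in severity of the most troubling symptom endorsed by the patient to 0-2 on the visual analog scale [none, mild or moderate".
- **Criteria for successful outcome.** "At least a third of patients fulfill criteria for primary outcome", which is 5 of the 15 evaluable patients sought.

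**The concern.** A reduction needs a starting value, and the Protocol does not say which rating supplies it. The wording of the follow-up paragraph implies an earlier round of the symptom scales, but the only earlier symptom rating described is the one that admitted the patient.

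That rating is a weak baseline. Entry needs 3 or more and response needs 2 or less, on the same labels, so a one-category slip from 3 to 2 meets the component. Patients selected because one rating was high tend to rate lower when asked again, treated or not. A patient already back at 2 before the first stimulation would count as reduced. No control arm is described that would show how much of this occurs.

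An analysis plan can say which rating is the baseline. It cannot supply a pre-treatment rating that was not taken, so the assessment list in the Protocol has to settle this.

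**Working it through.** **Reading.** The Protocol gives no calculation on this point, so there is no figure to reproduce. The passages fit together in two ways:

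1. A separate baseline rating is taken and is missing from the questionnaire list. The list then needs correcting, and the selection effect largely falls away.
2. The list is complete. The eligibility rating is then the baseline, and the figures below apply.

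**Assumed inputs (none is in the documents).** Rating = true level + independent normal error, rounded to 0–5. Total SD is 1, retest reliability r is 0.6, 0.7 or 0.8, and the mean before selection is 2.5 to 4.0. Patients enter if the screening rating is 3 or more. One follow-up visit is modelled. There were 2,000,000 simulated patients per cell before selection.

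**Share of enrolled patients meeting the symptom component with no true change** (r = 0.6 / 0.7 / 0.8):

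| Unselected mean | Follow-up 0–2, eligibility rating as baseline | Follow-up 0–2 and lower than a fresh pre-treatment rating |
|---|---|---|
| 2.5 | 29.6 / 25.3 / 20.5% | 16.9 / 14.1 / 11.0% |
| 3.0 | 18.7 / 16.1 / 13.0% | 12.0 / 9.9 / 7.6% |
| 3.5 | 10.3 / 8.9 / 7.3% | 7.3 / 6.0 / 4.6% |
| 4.0 | 4.7 / 4.2 / 3.4% | 3.7 / 3.0 / 2.3% |

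**Carrying this to the two-of-four rule.** Let p be the chance of meeting the symptom component and q the chance for each of the other three, taken as independent:

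P(responder) = p[1 − (1 − q)³] + (1 − p)[3q²(1 − q) + q³]

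- q = 0.20: 0.488p + 0.104(1 − p) = 0.104 + 0.384p
- q = 0.10: 0.271p + 0.028(1 − p) = 0.028 + 0.243p

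Trial success is the binomial chance of at least 5 responders among 15.

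- Mean 2.5, r = 0.6, q = 0.20: 0.104 + 0.384 × 0.296 = 0.218, so success without benefit is 21%. With the fresh rating, 0.104 + 0.384 × 0.169 = 0.169, giving 9%.
- Mean 3.0, r = 0.6, q = 0.20: 0.104 + 0.384 × 0.187 = 0.176, about 11%. With the fresh rating, 0.104 + 0.384 × 0.120 = 0.150, about 6%.
- Mean 3.5, r = 0.6, q = 0.20: 0.144, or 5.2%. With the fresh rating 0.132, or 3.8%.
- Mean 2.5, r = 0.6, q = 0.10: 0.028 + 0.243 × 0.296 = 0.100, or 1.3%. With the fresh rating 0.069, or 0.3%.
- For reference, p = 0 and q = 0.20 gives 0.104, or 1.5%.

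**Effect under a true one-category benefit.** The component is met by 59% instead of 69–73% (mean 2.5), 49–50% instead of 56–59% (3.0) and 37–38% instead of 41–43% (3.5). With the other components at 30%, the chance of at least 5 of 15 falls from 96–97% to 91–92%, from 90–92% to 85–86%, and from 78–80% to 73–74%. With the others at 20%, the largest fall is from 74% to 58% (mean 2.5, r = 0.6).

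**Separation of benefit from no benefit on the component** (arcsine difference) goes from 0.893 to 0.899 at mean 2.5, r = 0.6, and from 1.028 to 1.081 at mean 2.5, r = 0.8, the largest gain. It falls in no cell.

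**The case against.** The strongest reply is that the wording favours the harmless reading. The follow-up paragraph asks again for all three symptoms and calls the instrument a visual analog scale. The eligibility criterion needs only one symptom, never uses that term, and for fatigue grades loss of activity. This suggests an earlier round that a short list simply omits. The reply stands as a reason not to assume the worse reading. It does not settle the matter, because no earlier round is described anywhere.

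A reader might infer that no baseline exists at all, or that pre-treatment symptoms go unmeasured. The documents support neither. If a separate rating is intended, it may well be collected, and if not, the eligibility rating is a baseline, though a selected one. The Chalder also measures fatigue before treatment.

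A reader might also infer that drift alone could carry the trial to success. It cannot make anyone a responder, because a second component is required. An unselected mean of 2.5 may be too mild for patients still ill at least six months after infection who name the symptom as their major problem. At a mean of 3.5 the effect on the success rule is small. Independence of the components is itself an assumption, since the Chalder, the PGIC and a fatigue rating plausibly move together.

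Finally, counting reduction from a fresh rating mostly raises the bar and sharpens discrimination little. This is correct. The case for it is that it gives the reduction already required a starting point that did not select the patient.

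**Conclusion.** The point holds in a limited form. The list of pre-treatment assessments and the follow-up paragraph do not agree, and the starting point of a primary outcome component is left open. If the eligibility rating is the baseline, some regression to the mean can count as improvement: about 3% to 30% of patients on this component with no true change, under the assumptions above. The one-third rule is materially affected only toward a low unselected mean with the other components near 20%. In the most affected cell, success without benefit is 21%, against 9% with a fresh rating.

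These figures illustrate the mechanism and do not estimate the bias in this trial. The Protocol gives no mean, SD or reliability, and it does not strictly guarantee that the most troubling symptom started at 3, since only one symptom must reach that level. The two names for the index symptom, major problem at entry and most troubling symptom in the outcome, probably mean the same choice and only need to be tied together. The correction is worth considering in a 15-patient pilot, chiefly because it is cheap and has to be made before treatment starts.

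**What to change.** Reconcile the pre-treatment paragraph with the follow-up paragraph:

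- Add the three 0–5 symptom ratings to the pre-treatment assessments, with their recall period. Take them at the start of the existing Zoom session, before first stimulation.
- Record the most troubling symptom at that time and tie it to the major problem named at entry.
- Keep the 0–2 end state. Count the component when the follow-up rating of that symptom is 0–2 and lower than the pre-treatment rating.
- Keep all patients in the denominator. Do not also require the new rating to be 3 or higher, because that acts as a second selection and loses true responders.

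If such a rating is already taken, listing it and naming it as the baseline is enough. If the sponsor prefers the eligibility rating, the Protocol should say so and acknowledge the drift.

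The cost is three questions at an existing contact and a few lines of text. The component is met less often, also under true benefit (by about 10 to 14 percentage points at mean 2.5 and about 4 to 5 at mean 3.5). The change lessens regression to the mean but does not remove it, and it does not address natural recovery, which only a control arm can show.

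### Does the Chalder component misfire for patients who were not Chalder cases at entry?

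*Protocol*

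**What the plan says.** Under Inclusion Criteria the protocol states "To be included in the study, the patient must have at least one of the following": fatigue that substantially reduces activity, "brain fog producing at least a substantial burden over the past month", or "four quadrant pain producing at least a substantial burden over the past month". The threshold is a single rating, where "substantial is 3 or higher on a 0 to 5 scale". No entry criterion refers to the Chalder scale, which is completed as a questionnaire after consent: "Patients will complete the Chalder Fatigue Scale [11 questions with four possible answers each".

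The criteria for the primary outcome open with "Improvement on two of the following with improvement defined as" and list four components: a 0.6 SD change on SF-36 physical function; the patient's most troubling symptom falling to 0–2; "no longer a 'case' on the Chalder"; and a global impression of change of at least much improved. The trial counts as successful if at least a third of patients respond. The target is 15 evaluable patients, with up to 18 enrolled. The protocol states no null response rate, alpha or hypothesis test.

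**The concern.** The entry rule and the endpoint do not line up. The symptom-severity component follows whichever symptom troubles the patient most, and its target of 0–2 mirrors the entry threshold of 3, so it fits all three entry routes. The Chalder component concerns fatigue for everyone, although brain fog or pain alone is enough to enter.

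For a patient who is not a Chalder case at baseline, two scorings can be imagined:

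- **Free point.** Only follow-up status is looked at. The patient meets one of the two required components without changing, and needs just one of the other three.
- **Lost route.** Loss of caseness is required. The patient can never meet the component, and needs two of three where others need two of four.

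Either way the same rule sets a different hurdle for different patients, and the pooled rate depends partly on the mix at entry. With 15 patients the success line is 5 responders, so one or two patients can decide it, and a positive result is meant to lead straight to a grant application for a blinded trial.

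**Working it through.** The protocol gives no design calculation to reproduce. The check has two parts: what the words mean, and how much each scoring would matter.

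**Reading the text.** The four components sit under a lead-in that calls each one an improvement. Someone who was never a case has not improved by remaining a non-case and is not *no longer* a case. Both cues point to the lost-route scoring. The baseline Chalder needed to apply it is collected.

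**Who is affected.** The dividing line is Chalder caseness at baseline, not the symptom used for entry. A patient who enters on brain fog or pain may well be a case, and one who enters on the 0–5 fatigue rating is not guaranteed to be. The number of non-cases cannot be derived from the protocol. Its background lists fatigue first among the common symptoms and says that many such patients met criteria for chronic fatigue syndrome, which suggests non-cases would be a minority.

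**Size.** From the protocol: two of four components; success at 15/3 = 5 responders. Assumed: each component is met with the same chance p in the absence of benefit, and non-cases stay non-cases. With independent components and q = 1 − p:

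- case, two of four: 6p²q² + 4p³q + p⁴
- non-case, lost route, two of three: 3p²q + p³
- non-case, free point, one of three: 1 − q³

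At p = 0.20:

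- 0.1536 + 0.0256 + 0.0016 = 18.1%
- 0.0960 + 0.0080 = 10.4%
- 1 − 0.512 = 48.8%

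Components are probably positively correlated. With a common latent correlation of 0.3 (Gaussian copula, solved by numerical integration) these three become 21.2%, 14.1% and 43.0%.

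The chance of at least 5 responders among 15 comes from convolving the two kinds of patient. At p = 0.20:

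| Non-cases among 15 | Lost route, corr. 0 | Free point, corr. 0 | Lost route, corr. 0.3 | Free point, corr. 0.3 |
|---|---|---|---|---|
| 0 | 11.8% | 11.8% | 19.6% | 19.6% |
| 1 | 10.7% | 16.3% | 18.3% | 23.7% |
| 2 | 9.7% | 21.8% | 17.0% | 28.1% |
| 5 | 6.9% | 42.5% | 13.5% | 43.1% |

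At p = 0.15 and correlation 0.3, with five non-cases, the figures are 3.3% (lost route) and 18.5% (free point), against 5.4% if all are cases.

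On the lost-route reading at p = 0.20 and correlation 0.3, false success falls by 19.6 − 18.3 = 1.3 points with one non-case, 19.6 − 17.0 = 2.6 with two, and 19.6 − 13.5 = 6.1 with five. Every large upward shift belongs to the free-point scoring.

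**What a rewording would do.** Defining the component as a case at baseline and not a case at follow-up writes out the lost-route reading. The lost-route columns would stand as they are, and non-cases would still face two of three.

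**SF-36.** The physical-function component is a change of 0.6 SD, so an unimpaired patient gains nothing without changing. At most there is a ceiling on how far that patient can improve, and the Chalder argument does not carry over.

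**The case for a change.** The best counter-argument is that the responder definition and the success rule are fixed in the protocol itself, and neither says how a baseline non-case is scored. Nothing expressly forbids scoring follow-up status alone. If that were done, even two non-cases would raise the chance of false success from 19.6% to 28.1% under the assumptions above, in a trial that one or two patients can decide. One sentence would exclude it, at no cost in data.

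Part of this stands: the entry rule and the component are not matched, and explicit wording would be tidier. But the free point requires an analyst to call someone improved, and no longer a case, who never was one. Wording that already points away from that reading does not need an amendment to exclude it, and spelling out the scoring of such patients is the kind of detail an analysis plan, not shown here, commonly holds.

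The other half of the complaint, the unequal hurdle, would survive the sentence. To remove it, entry would have to be limited to Chalder cases, which narrows the population the pilot set out to study, or the component would have to be dropped for everyone. Neither is an obvious gain: patients without caseness keep three components that apply to them, one of which tracks their own most troubling symptom.

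**Conclusion.** The mismatch between entry and endpoint is real, but no change to the plan follows. On the natural reading, a patient who is not a Chalder case at baseline cannot meet this component and must meet two of the other three. That makes success slightly harder to claim: about 1 to 3 percentage points lower with one or two such patients, and about 6 points lower with five of 15, at an assumed 20% chance per component and correlation 0.3. In an uncontrolled pilot without a stated error rate, a small error in the cautious direction is acceptable.

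The figures near 43% depend on a strained scoring and on an assumed five non-cases, so they do not describe the plan as written. The conclusion rests on the analyst taking the component in its ordinary sense. How many patients it could not apply to can be read from the baseline Chalder scores already collected.

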Unfortunately, efforts to get NIH funding for a blinded follow up study were unsuccessful. Therefore, [name] applied for and got funding to use VNS to try to reduce the widespread pain reported by many Gulf War veterans using transcutaneous VNS to the left vagus. Unfortunately, the results of that study were negative⁵. We believe the reason for this lack of effect was that the amount of stimulation in the tVNS study was only 12 min while that for the implanted VNS study was 144 min. Fortunately, the device used in the study on Long Covid clipped to the tragus of the ear and allowed stimulation for 35 min a day over the 10 days of study. We believe the difference in outcome between our own Gulf Vet study and this one on Long Covid has to do with amount of stimulation delivered and the fact that auricular VNS targets afferent fibers only while cervical VNS activates both afferent and efferent fibers. We propose using the same device used in the Long Covid study here. Importantly the transcutaneous device that stimulates the auricular branch of the vagus has been designated non-significant risk (NSR) by the FDA [This designation was given in the process of US regulatory work by the manufacturer]. Therefore this proposed trial will not require any interaction with FDA.

This will be an investigator-initiated pilot study seeking evaluable data on 15 subjects; we are asking the IRB permission to enroll up to 18 subjects in case of drop out. If the outcome is positive, [name] will immediately use the results to write an RO1 to do a blinded trial of VNS in Long Covid.

Effective Date: 3/8/2022 End Date:3/7/2023

ResearchMatch will be used as a method for identifying and contacting potential subjects. The study specific announcement is included with this submission.

Inclusion Criteria

- Patient had a history compatible with COVID-19 infection at least 6 months previous to today.
- Patient was not admitted to an ICU and did not require oxygen supplementation if hospitalized
- Patient did not have organ pathology during COVID-19 such as pneumonia.
- Patient has been cleared by primary care provider or specialist as having no medical explanation for their symptoms and signs and has had a recent normal ECG (within 4 months).

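### The only secondary outcome cuts the POMS score into yes/no at 10 points, discarding over a third of its information on mean change and leaving the pilot's defined outcomes without a mean or an SD

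*Protocol*

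**What the plan says.** The Protocol has no numbered sections. The design paragraph before the Inclusion Criteria describes a single-arm pilot: "This will be an investigator-initiated pilot study seeking evaluable data on 15 subjects". Its purpose, if the result is positive, is that the investigator "will immediately use the results to write an RO1 to do a blinded trial of VNS in Long Covid".

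The paragraph after the Inclusion Criteria sets the entry questionnaires: "Patients will complete the Chalder Fatigue Scale [11 questions with four possible answers each]; Short Profile of Mood States [37 words" and so on, followed by the SF-36. The follow-up paragraph repeats all three at two calls and adds symptom ratings: "Patients will be called at 4 and 6 weeks after starting treatment and will again be asked to provide data on the visual analog scales". The global impression of change is asked only after treatment.

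The outcome paragraphs then define three things, all of them yes/no:

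- **Primary:** at least two of four criteria met, one of which is "a 0.6 SD reduction in impaired physical function on the SF-36".
- **Secondary:** "Criterion for secondary outcome: Improvement by at least 10 points on the short version of the POMS".
- **Trial success:** at least a third of patients meeting the primary.

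No outcome is a mean change, and no SD or confidence interval is mentioned.

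**The concern.** A scored questionnaire taken before and after treatment shows how far each patient moved. A 10-point cut keeps only which side of a line the patient fell on: a 9-point improvement and a worsening both count as failures. With 15 patients there is little information to spare.

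The pilot is also meant to feed a later trial. A responder share alone does not tell the reader whether the typical change was large and consistent or small and scattered. For the secondary outcome, where nothing but the score is involved, the more informative definition was available at no cost in data.

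**Working it through.** **Inputs from the Protocol:** 15 evaluable patients, a POMS cut of 10 points, and a success benchmark of one third for the primary (used below only as a convenient responder share). The Protocol gives no SD, effect size, alpha or power, so there is no planned figure to reproduce.

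**Assumptions:** the POMS change score is normally distributed. In step 1 its SD is treated as known, which favours the count.

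**Step 1: information kept by one cut.** If a share p responds, the count estimates p with variance p(1−p)/n. A shift of the mean moves p at rate φ(z_p)/SD. Relative to the sample mean, whose variance is SD²/n, the efficiency is

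E = φ(z_p)² / [p(1−p)], and the effective n is 15 × E.

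| Share responding | E | Effective n of 15 |
|---|---|---|
| 10% or 90% | 0.342 | 5.1 |
| 20% or 80% | 0.490 | 7.4 |
| 25% or 75% | 0.539 | 8.1 |
| 33% or 67% | 0.595 | 8.9 |
| 50% | 0.637 | 9.5 |

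Even at the most favourable cut, 36% of the information is lost.

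**Step 2: small-sample check.** For a standardised mean change of 0.8 at n = 15 (two-sided 5%), the paired t-test has 82% power and the exact sign test 60%; a t-test on only 10 patients has 62%. At 0.6 the three figures are 58%, 38% and 40%. The sign test cuts at zero rather than at 10 points, and its attained level is 3.5%, so part of the gap is discreteness. The order of loss agrees with step 1.

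**Step 3: what a responder share says about the change.** With one third falling by at least 10 points, the mean fall is 10 − 0.431 × SD:

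| Assumed SD (points) | Mean fall (points) | Mean fall / SD |
|---|---|---|
| 5 | 7.9 | 1.57 |
| 10 | 5.7 | 0.57 |
| 15 | 3.5 | 0.24 |
| 20 | 1.4 | 0.07 |

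The same count fits a very large standardised effect or almost none. The share itself is loosely known: 5 of 15 has an exact 95% CI of 11.8% to 61.6%.

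**Step 4: what the score would give.** The 95% CI half-width for the mean change is t(0.975, 14)/√15 = 2.145/3.873 = 0.55 SD. The 95% limits for the SD are √(14/26.12) = 0.73 and √(14/5.63) = 1.58 times the estimate.

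**The case against.** The strongest reply is that nothing is lost from the data. The raw scores are kept, nothing excludes a table of mean changes, and a statistical analysis plan that is not shown may provide one. It stands that the loss is recoverable. But the Protocol itself defines the outcomes, and it defines the only secondary as a cut. A mean change introduced elsewhere would not be a protocol-defined outcome.

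A second reply is that the pilot's decision is whether a third of patients respond, which a count answers directly. That stands for the primary, and is why the primary should be left alone. It does not explain a yes/no secondary on which no decision rule rests.

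A reader might infer three stronger claims that the Protocol does not support:

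- **That all outcomes reduce 15 patients to 8 to 10.** The primary is two of four criteria, not one score cut once, and includes a global rating with no pre-treatment value. Its loss cannot be derived from the Protocol. Nor can a figure be read off the SF-36 criterion, because the text does not say which SD its 0.6 refers to.
- **That the plan pushes the blinded trial towards a responder endpoint, or leaves it impossible to size.** The Protocol names no endpoint or sizing method for that trial, and a responder trial could be sized from proportions. An SD from 15 patients is itself a weak basis: sample size scales with its square, so limits of 0.732 and 1.577 become factors of 0.54 and 2.49.
- **That patients with low mood disturbance will be wrongly counted as failures.** Entry requires a substantial fatigue, brain-fog or pain burden but no minimum POMS score, so this is possible. No baseline POMS values are given, so it cannot be shown.

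**Conclusion.** The point holds for the secondary outcome and is minor. Under a normal change score and a 25% to 75% responder share, the 10-point cut leaves 15 patients worth about 8 to 9.5 for estimating a mean shift; at 10% to 20% responding (or 80% to 90%) this falls to about 5 to 7. Without an SD, the count cannot separate a mean fall of 7.9 points from one of 1.4 points over the SD range assumed here. No other outcome fills the gap, since all are yes/no. The primary composite and the success rule are not faulted here, and no consequence for the design of the later trial is claimed.

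**What to change.** Keep the composite primary and the one-third success rule. Then:

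- Define the secondary outcome as the mean within-patient change in short POMS total from baseline to week 4 and to week 6, with SD and 95% CI (paired t). Report the 10-point count beside it.
- Add the same summary for SF-36 physical function and Chalder total.
- State that the mean changes are descriptive, because there is no control arm, and that the SDs may inform the sizing of the blinded trial but are imprecise (95% limits about 0.73 to 1.58 times the estimate at 15 patients).

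The cost is a short edit to the outcome paragraph and one results table. No visit, instrument or patient is added. The only downside is a few more descriptive estimates to report.
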